## 5.6 Treatment Compliance

Treatment in HOPE-Duchenne is a one-time procedure. Therefore, continued compliance with the investigational product is not applicable. Study site personnel will document compliance with any concomitant medications and study follow-up procedures at each study visit.

CCI

[REDACTED]

[REDACTED]

[REDACTED]

[REDACTED]

[REDACTED]

[REDACTED]

CCI

## 5.9 Investigational Product Retention at Study Site

Since product will be delivered as-needed on a per subject basis, there will be no product to retain at the site.

## 6 STUDY PROCEDURES

### 6.1 Informed Consent

All subjects that are at least of 18 years of age must provide written consent prior to performing any study-related procedure. All subjects that are at least 12 years of age, but less than 18, must provide written assent along with parental or guardian written permission prior to performing any study-related procedure. An Informed Consent Form (ICF) will be provided to an adult subject for their consideration. An Assent Form (AF) will be provided to an adolescent subject and the subject's parent(s) or guardian(s) for their consideration. Each form will contain all United States federally required elements, all ICH-required elements, and Health Insurance Portability and Accountability Act (HIPAA) authorization information in language that is understandable to the subject and subject's parent(s) or guardian(s), if applicable. The process of obtaining informed consent or assent will be in compliance with all federal regulations, International Conference on Harmonisation (ICH) requirements, and local laws.

The Investigator and/or designee must discuss the study with each subject and the subject's parent(s) or guardian(s), if applicable. The discussion will include the nature, scope, procedures, and possible consequences of the subject's participation in the study. The ICF/AF and discussion will be in a form understandable to the subject and the subject's parent(s) or guardian(s). The subject and subject's parent(s) or guardian(s) must be given adequate time to review the ICF/AF and ask questions regarding the IP, procedures, risks and other treatment. For subjects at least 18 years of age, an ICF must be signed and dated by the subject and the Investigator or designee before participation in the study. For subjects that are at least 12 years of age, but less than 18, an AF must be signed and dated by the subject, the subject's parent(s) or guardian(s), and the Investigator or designee before the subject can participate in the study. The subject will receive a copy of the signed and dated ICF, and the original will be retained in the site study files. The subject and parent(s) or guardian(s) will receive a copy of the signed and dated AF, and the original will be retained in the study site files. The Investigator or designee will emphasize to the subject and subject's parent(s) or guardian(s) that study participation is entirely voluntary and that consent and/or assent regarding study participation may be withdrawn at any time without penalty or loss of benefits to which the subject is otherwise entitled.

Modifications to the study design, adjustments to the method of study conduct, or release of new safety information may occur during the course of the study that may require an amended ICF and/or AF. The amended ICF and/or AF will contain all United States federally required elements, all ICH-required elements, and Health Insurance Portability and Accountability Act (HIPAA) authorization information in language that is understandable to the subject and subject's parent(s) or guardian(s). The site must use the amended ICF and/or AF for all new subjects. All ongoing subjects must repeat the consent and/or assent process with the Investigator or designee using the amended ICF and/or AF.

Ongoing subjects that mature to at least 18 years of age during the course of the study may be required to provide written informed consent (i.e., ICF) depending on the requirements of the reviewing IRB, as well as local regulations.

## **6.2 Medical History & Concomitant Medications**

The general and cardiac-specific medical histories (e.g., significant procedures, medications, therapies, allergies) of subjects randomized in the study will be documented as part of the Screening Visit and reviewed during all subsequent visits for any modifications (i.e., assessment for potential adverse events). General and cardiac health, as well as concomitant medications, will be reviewed and assessed at each visit and new information will be updated in the subject's study documentation.

## **6.3 Cardiac and Limited Physical Examinations**

A qualified physician, either the Investigator or Sub-Investigator, will perform a cardiovascular physical examination at each study visit.

A limited physical examination will be conducted at the screening visit and the 12 Month follow-up visit.

Weight and height will be collected at Screening, 6-month, and 12-month visits. Height alone will also be assessed at the 6-week and 3-month visits. If standing height cannot be measured, height will be calculated using a measurement of ulna length (Gauld et al 2004).

## **6.4 Vital Signs**

Temperature, heart rate (seated), blood pressure (seated) and respiration rate will be recorded at each visit.

## **6.5 Clinical Laboratory Tests**

### **6.5.1 Laboratory Parameters**

Clinical laboratory tests will include those listed in 6.10.1 CAP-1002 Infusion, Appendix 1 (Schedule of Events), and Appendix 2 (Clinical Laboratory Tests). Subjects will be in a seated or supine position during blood collection.

### **6.5.2 Sample Collection, Storage, and Shipping**

All clinical laboratory testing in this trial will be performed by central laboratory facilities, except those performed on Days 0 and 1 for subjects randomized to CAP-1002 only. All samples will be collected, processed, stored and shipped (as applicable) according to instructions in the Clinical Laboratory Manual for this trial.

For subjects randomized to CAP-1002, the clinical site should collect and process samples for the following tests in accordance with their institutional policies to appropriately monitor subject safety pre and post infusion:

**Table 2. Local Laboratory Testing, Day 0 and Day 1 (CAP-1002 Arm Only)**

Pre-Infusion	Post-Infusion
Troponin I	Troponin I ( serial collection )
CK-MB	CK-MB ( serial collection )
Serum Chemistry*	Serum Chemistry*
Hematology*	Hematology*
Urinalysis*	Urinalysis*
PTT & INR (if taking warfarin)	

\*See Appendix 2 for details

Serum for the donor specific antibody (DSA) monitoring, HLA typing and blood for the ELISpot assay will be collected and processed at each site and then shipped to a central core laboratory for analysis within 24 hours of obtaining the specimens (See Laboratory Manual for shipping instructions). Subjects will be monitored for the development of a cellular immune response using the ELISpot (enzyme-linked immunosorbent spot) assay. The ELISpot assay will be performed at screening and at the Week 6 study visit.

Serum for research purposes (biomarkers) will be collected and processed at each site then shipped to a central core lab that will then ship to Capricor for final storage and analysis (if subject has provided consent).

For subjects who provide consent and/or assent, serum for clinical research into biomarkers will be collected at every scheduled visit (excluding infusion) and sent to the Sponsor, or designee, for storage and/or analysis (including and future analysis). Per the Code of Federal Regulations (21 CFR 320.38), serum samples collected from study subjects will be maintained in storage for at least five (5) years following the date on which the IND application or supplemental application is approved. If such application or supplemental application is not approved, serum samples will be maintained in storage for at least 5 years following the date of completion of the clinical research study.

## 6.6 12-Lead ECG

Beginning at the screening visit, a 12-Lead ECG will be performed at every study visit to assess for rhythm disturbances and new myocardial ischemia or infarction. Subsequent ECGs will be compared with the screening ECG for any changes in rhythm and conduction. All changes and any associated clinical significance will be evaluated and documented on the case report forms.

## 6.7 Continuous Cardiac Rhythm Monitoring

The sponsor will provide a wearable, wireless device for continuous cardiac rhythm monitoring. Subjects will wear a monitoring device for defined short-term intervals, starting at screening, on Day 1, and at the Week 6, Month 6, and Month 12 study visits. Table 3 details the continuous monitoring duration required at each study visit. The monitoring is

used to detect and record arrhythmias. All changes and any associated clinical significance will be evaluated and documented on the case report form.

**Table 3. Per-Visit Minimum Continuous Cardiac Monitoring Durations**

Study Visit	Minimum Continuous Monitoring Duration
Screening	24 hours
Day 1	72 hours
Week 6	72 hours
Month 6	7 days
Month 12	72 hours

## **6.8 Magnetic Resonance Imaging**

All subjects will undergo contrast-enhanced MRI at screening and the Month 6 and 12 study visits (or, Early Termination Visit). It is anticipated that the duration of each MRI session will be 45-60 minutes. Acquisition parameters and techniques are specified in the MRI Imaging Manual. The site-based MRI technologists will be trained and certified in the common acquisition protocol prior to initiation of enrollment at each site.

### **6.8.1 Cine Imaging Protocol**

A cine imaging protocol will be utilized for global ejection fraction and LV volumes and mass determination. Acquisition parameters and techniques are specified in the MRI Imaging Manual. The site-based MRI technicians will be trained and certified in the common acquisition protocol prior to initiation of enrollment at each site.

### **6.8.2 Delayed Contrast-Enhancement Protocol**

Subjects will undergo a standardized acquisition protocol including an intravenous injection of gadolinium contrast as defined in the MRI Imaging Manual consistent with institutional guidelines.

### **6.8.3 Image Analysis**

All study images and applicable imaging data will be sent to and centrally read at an independent imaging core by cardiovascular radiology experts. MRI will be performed on standard phantoms for quality assurance and to detect any changes in system sensitivity over time.

### **6.8.4 Historical Cardiac MRI**

If a subject has a historical cardiac MRI scan available prior to Screening date, the site should request that this historical cardiac MRI be sent to the imaging core lab for this trial, to potentially determine the rate of cardiac disease progression at the time of screening. If

multiple historical cMRIs are available, the most recent scan that occurred at least 6 weeks prior to screening should be transferred.

## 6.9 Clinical Function and Quality of Life Measures

At the screening, 6 Weeks, 3 Months, 6 Months, and 12 Months (or Early Termination) study visits, the subject will be asked to complete the Performance of Upper Limb (PUL) assessment and spirometry. Both the subject and the parent/guardian will be asked to complete the Pediatric Quality of Life Inventory (PedsQL) and the PODCI Adolescent Questionnaire (PODCI).

In addition, subjects assessed by the Investigator as capable of performing the Six Minute Walk Test (6MWT) will do so at screening, 6 Weeks, 3 Months, 6 Months, and 12 Months (or, Early Termination) study visits. Subjects unable to perform the Six Minute Walk Test at screening will not be required to perform the test at any subsequent visit.

## 6.10 Infusion Procedure

### 6.10.1 CAP-1002 Infusion

Every attempt should be made to infuse the three major cardiac territories of the left ventricle (anterior territory, lateral territory, and inferior/posterior territory). Additionally, the infusing Investigator may alter the infusion plan during the infusion procedure when deemed clinically necessary. The procedure will be performed as follows:

CCI

A large block of text has been redacted with a black rectangular box. The redacted text begins with the acronym 'CCI' in red, followed by several lines of blacked-out text. The redacted area is approximately 10 lines high and 80 characters wide.

CCI

Following intracoronary infusion, subjects will be observed in the hospital for 20-24 hours with continuous cardiac (telemetry) monitoring. Troponin and CK-MB laboratory studies and vital signs (temperature, HR, BP, and RR) will be monitored every 8 hours ( $\pm 30$  minutes) from the end of the infusion. A total of three sets of cardiac enzymes will be evaluated to rule out cardiac injury during the post-infusion hospital stay through discharge. If the subject is discharged prior to 24 hours, cardiac enzymes will be drawn just prior to discharge.

Prior to discharge from the hospital, a physical assessment will be performed which will include chest pain assessment, review of laboratory results, 12-lead ECG, and arterial puncture site as well as assessment of adverse events. In the absence of serious adverse events, subjects will be discharged per standard of care practice.

#### 6.10.2 Infusion Procedure Stopping Criteria

The operator will continuously monitor for the following Stopping Criteria. If any Stopping Criteria are met, the infusing Investigator must stop the infusion and assess for clinical significance. The infusing Investigator may continue with the infusion if, based on the infusing Investigator's medical judgement and clinical context, no additional risk is presented to the subject.

1. Development of TIMI flow 0-2 or TIMI myocardial perfusion grade (TMPG) 0-2 persisting for  $>3$  minutes after a cycle of infusion, despite administration of intracoronary vasodilators;
2. Sustained hypotension unresponsive to fluids and/or atropine/vasopressor administration;
3. Evidence of cerebrovascular accident;
4. Evidence of cardiac tamponade;
5. Hemopericardium requiring pericardiocentesis;

6. Sustained VT/VF that requires cardioversion/defibrillation or administration of an antiarrhythmic;
7. Evidence of thrombus in the aorta that was not previously seen;
8. Suspected or confirmed aortic dissection;
9. Suspected or confirmed coronary dissection;
10. Other evidence of acute myocardial infarction;
11. Acute onset of rigors (symptoms indicative of acute sensitivity or infection).

## 7 STUDY ACTIVITIES

Refer to Appendix 1 for the Schedule of Events for the conduct of this study.

### 7.1 Screening Visit

Written informed consent or assent must be obtained from the subject prior to performing any study-related tasks. Afterwards screening period for that subject will begin and the following screening procedures will be performed (not more than 30 days prior to randomization):

- Review of Inclusion / Exclusion Criteria (Section 4.2 and Section 4.3)
- Collection of demographic information
- Review of medical and cardiac history, and concomitant medications
- Measurement of vital signs (body temperature, HR, BP, and RR), weight and height
- 12-lead ECG
- 24-hour ECG via sponsor-provided continuous cardiac rhythm monitoring system
- Cardiac and limited physical examination
- Cardiac MRI
- Venous blood will be collected for the following:
  - Clinical laboratory tests: serum chemistry, hematology, and serology (HbsAg, anti-HCV, anti-HIV 1/2), Cystatin C, Troponin and CK-MB
  - Biomarkers: Osteopontin, ST2, IL-10, and Galectin-3
  - Exploratory biomarkers (if consent/assent provided)
  - Immunoassay: HLA, DSA, and ELISPOT
  - See 6.5 for additional information on clinical laboratory testing.
- A urine sample will be collected for urinalysis
- PUL Scale
- 6MWT (if capable)
- Pediatric QoL Inventory (PedsQL)
- PODCI
- Spirometry
- Adverse Event Assessment
- Submission of historical cardiac MRI

Subjects must continue to meet all of the inclusion and none of the exclusion criteria before proceeding to randomization. Subjects who do not proceed to randomization for any reason during screening will be withdrawn from the study as screen failures and will have no further follow up.

## 7.2 Randomization, Day 0, and Day 1

Subjects that continue to meet eligibility will be randomized (1:1) to either the active treatment arm (CAP-1002) or usual care arm.

For subjects that are randomized to the usual care arm, Day 0 will be defined as seven (7) days after the date of randomization. For subjects that are randomized to the active treatment arm, Day 0 will be defined as the date of the intracoronary infusion of CAP-1002.

**For subjects randomized to CAP-1002 only**, the infusion visit will include tests and assessments as described below and in accordance with the site's standard operating procedures.

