### Duration of Follow-Up:

All randomized subjects will be followed out to one year post-Day 0. Annual follow-up phone calls will be conducted for an additional four years after this time for subjects that provide consent and/or assent. These annual follow-up phone calls will continue in concert with a subject’s normal, annual clinical follow-up which may include annual cardiac MRI where clinically indicated.

Due to the small size of the trial population, continued participation for all subjects is crucial to data quality. Therefore, no subject will be assessed as “Lost to Follow-Up” unless the site has attempted to contact the subject (or parent/guardian) by phone (or email or other subject-preferred method of communication) on at least 3 different days, plus an attempt to contact the subject (or parent/guardian) by certified mail.

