### 3 INVESTIGATIONAL PLAN

#### 3.1 Overall Study Design and Plan

Male subjects with cardiomyopathy secondary to DMD meeting all inclusion and no exclusion criteria will be randomized. All subjects will be at least 12 years of age. They will be randomized in a 1:1 manner to either intracoronary infusion of CAP-1002 in three coronary arteries supplying the three major cardiac territories of the left ventricle of the heart (anterior, lateral, inferior/posterior) or usual care. In the active treatment arm, all three major cardiac territories will be treated (infused) during a single procedure in an open-label fashion.

Approximately 24, and not more than 30, subjects will be randomized into the study, in two sequential enrollment groups. Safety data from Group 1 will undergo a Data Safety Monitoring Board (DSMB) review prior to initiation of enrollment for Group 2.

The first 6-8 randomized subjects will comprise Group 1, and will include a minimum of 3 subjects completing intracoronary infusion with CAP-1002. The DSMB will conduct a review of interim safety data through 72 hours post-Day 0 for at least 3 infused subjects and for at least 6 subjects overall.

Enrollment of Group 2 will begin per DSMB recommendations following their review of the 72 hour safety data from Group 1. Group 2 will include approximately 18 subjects. Screening and randomization will continue until a total of 12 subjects are infused with CAP-1002 or 30 subjects are randomized into the study, whichever comes first.

CCI

A large rectangular area of the page is completely blacked out, indicating redacted content. The text 'CCI' is printed in red at the top left corner of this redacted area.

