## Appendix 1 Schedule of Events

Procedure / Event	Screening	Infusion (CAP-1002 only) 		Day 1 (Home)	Day 3 (Phone)	Week 2	Week 6	Month 3	Month 6	Month 12	Early Termination 
Study Day	≤30 days prior to randomization	Day 0		Day 1 	Day 3 (+3)	Day 14 (±3)	Day 40 (±7)	Day 90 (±7)	Day 180 (±14)	Day 360 (±30)	As Needed
		PRE	POST								
Informed Consent	X										
Eligibility Assessment	X	X									
Demographics	X										
Medical History	X	X									
Cardiac History	X	X									
Concomitant Medications	X	X	X			X	X	X	X	X	X
Vital Signs	X	X	X			X	X	X	X	X	X
Weight	X								X	X	X
Height 	X						X	X	X	X	X
12-Lead ECG	X	X	X			X	X	X	X	X	X
Limited Physical Examination	X									X	X
Cardiac Physical Examination	X	X	X			X	X	X	X	X	X
Cardiac MRI	X								X	X	X
Continuous cardiac rhythm monitoring	X			X			X		X	X	X
Clinical Laboratory Tests (includes Chemistry, Hematology, Urinalysis)	X	X	X			X	X	X	X	X	X
Serology 	X										
Osteopontin	X					X	X	X	X	X	X
ST2	X					X	X	X	X	X	X
IL-10	X					X	X	X	X	X	X
Galectin-3	X					X	X	X	X	X	X
Exploratory Biomarkers	X					X	X	X	X	X	X

Procedure / Event	Screening	Infusion (CAP-1002 only) 		Day 1 (Home)	Day 3 (Phone)	Week 2	Week 6	Month 3	Month 6	Month 12	Early Termination 
Study Day	≤30 days prior to randomization	Day 0		Day 1 	Day 3 (+3)	Day 14 (±3)	Day 40 (±7)	Day 90 (±7)	Day 180 (±14)	Day 360 (±30)	As Needed
		PRE	POST								
HLA	X										
DSA	X					X	X	X	X	X	X
ELISpot	X						X				
PUL scale	X						X	X	X	X	X
6MWT	X						X	X	X	X	X
Pediatric QL Inventory	X						X	X	X	X	X
PODCI	X						X	X	X	X	X
Spirometry	X						X	X	X	X	X
Coagulation		X									
Serum Troponin & CK-MB	X	X	X			X			X	X	X
Intracoronary Infusion			X								
Adverse Event Assessment	X	X	X		X	X	X	X	X	X	X

 Day 0 is the infusion date for subjects randomized to CAP-1002. All items listed for Infusion visit and assessments on Day 0 are only applicable for subjects randomized to CAP-1002. Subjects randomized to Usual Care do not have a Day 0 visit.

 Early Termination Visit procedures to be completed at time of withdrawal, should subject be withdrawn before Month 12 Visit. A Cardiac MRI will be conducted provided the subject's most recent study-related Cardiac MRI was conducted at least three months (i.e., 12 weeks) prior to the Early Termination Visit.

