### 7.3 Data Analysis

- The anchor date used for summaries and analyses will depend on the analysis population, as follows:
  - ITT population: randomization date
  - mITT population: IP administration or reference date

- Safety population: IP administration or reference date
- Per protocol population: IP administration or reference date
- Categorical variables will be summarized as frequencies and percentages in each category. Percentages will be reported to one decimal place. Unless otherwise noted in Sections 8-10, categorical variables will be analyzed using chi square tests of association or, if any contingency table cell has less than 5 subjects, Fisher's exact test.
- Continuous variables will be summarized by numbers of subjects, means, standard deviations, medians, and ranges. The number of decimal places for minimums and maximums will be the same as the original data. The number of decimal places for means, medians, and interquartile ranges will be the same as the original data plus one. The number of decimal places for measures of variance will be the same as the original data plus two. Unless otherwise noted in Sections 8-10, continuous variables will be analyzed using t-tests or, if appropriate, analysis of covariance with baseline as a covariate. Non-parametric tests and data transformations will be considered for variables with distributions that violate parametric assumptions.
- Data with qualifiers (e.g., “<”) will be listed with but summarized without the qualifier.
- P-values will be presented to two decimal places if  $> 0.01$ , to three places if  $< 0.01$  but  $> 0.001$ , and to four places if  $< 0.001$  but  $> 0.0001$ . P-values  $< 0.0001$  will be presented as “ $< 0.0001$ .”
- Statistical tests will be two-sided and tested at the 0.05 significance level unless otherwise noted in Sections 8-10.
- It is understood that statistical non-significance is not an indicator of equivalence.

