## 7.6 Study Period and Time Point Definitions

The following study periods and time points are defined:

Screening Period: the 30-day time period before IP infusion or the reference time point.

Baseline: for a given parameter for a given subject, the last observation before IP infusion or the reference time point.

Day 0: for a given subject, the day of planned IP infusion or the reference day.

(Nominal Visit) Analysis Time Point: analysis based on data collected at the *(nominal visit)* time point, where nominal visits are as shown below in [Section 7.7](#).

End of Study (EOS), Subject Level: subject-level EOS is reached after completion of the Month 12 visit or discontinuation for any reason.

EOS, Study-Level: EOS is reached when all randomized subjects have either completed the Month 12 visit or have discontinued from the study for any reason.

Long-Term Follow-Up (LTFUP) Period, Subject-Level: the LTFUP period begins after completion of the Month 12 visit and continues until 4 more annual visits have been completed.

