where  $X(t_i)$  is observed LGE at  $t_i$ ,  $R(t_i)$  is observed LGE at the reference time point for  $t_i$ , and  $D(t_i)$  is the number of days between  $t_i$  and the reference time point for  $t_i$ . The reference time point will be the date of historical MRI for  $i = 1$  and baseline for  $i > 1$ . The mixed effects model to be used for the final analysis will be similar to that described above, with historical LGE included as a covariate. The LSMEANS procedure in PROC MIXED will be used to compare  $RC(t_2)$  and  $RC(t_3)$  to  $RC(t_1)$  within each treatment group, and tests for interaction along with descriptive statistics will be used to evaluate differences by treatment group.

Assuming missing observations are “missing at random” (MAR), i.e., the fact that they are missing is unrelated to the missing variable but can be related to another variable on which data have been collected, the maximum likelihood (ML) approach is able to handle subjects with either Month 6 or Month 12 changes from baseline missing, but not both. Therefore, for final analyses based on the mITT population, missing data will be addressed using ML. Final analyses based on the ITT population may include subjects with both Month 6 and Month 12 changes from baseline missing; under these circumstances, multiple imputation will be used based on all observations and will use a fully conditional specification method with 20 burn-in iterations and the regression method of imputation. Variables in the imputer’s model will be baseline observation (because baseline is used as a covariate in analyses), Month 6 change from baseline, Month 12 change from baseline, and treatment group. Because the MAR assumption is not testable, and because it seems possible that subjects with poorer outcome may be more likely to miss trial assessments, a sensitivity analysis under a “missing not at random” (MNAR) assumption may be done (for the final analysis only) for any efficacy endpoint for which all change from baseline measurements are missing for some subjects. For the MNAR model, multiple imputation will use the pattern-mixture model approach to address missing values; i.e., the imputation will be based on a pre-specified subset of subjects: for this MNAR analysis, only subjects randomized to usual care. Because very few missing observations are expected in this trial, 5 imputed data sets will be used for all analyses using multiple imputation.

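### A CAP-1002 subject who is never infused has no protocol Day 0, and if he lacks both Month 6 and Month 12 values, any ITT imputation gives him roughly the infused-arm mean

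*Protocol*

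**What the plan says.** **Day 0.** Protocol 7.2 ties the active-arm Day 0 to the infusion itself: "For subjects that are randomized to the active treatment arm, Day 0 will be defined as the date of the intracoronary infusion of CAP-1002". Footnote 1 of Appendix 1 repeats this: "Day 0 is the infusion date for subjects randomized to CAP-1002". The control arm has a date that needs no procedure: "For subjects that are randomized to the usual care arm, Day 0 will be defined as seven (7) days after the date of randomization". All later contacts are counted from Day 0, and the Synopsis (Duration of Follow-Up) says: "All randomized subjects will be followed out to one year post-Day 0".

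SAP 7.6 defines Day 0 differently, as "for a given subject, the day of planned IP infusion or the reference day". It also defines Baseline as the last value before infusion or the reference time point, and SAP 2.3.1 gives that time point for usual care subjects only. SAP 7.3 lists "ITT population: randomization date" as the ITT anchor, but SAP 7.7 then subtracts X, the days from randomization to Day 0.

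**Who may be uninfused.** Protocol 3.1: "Screening and randomization will continue until a total of 12 subjects are infused with CAP-1002 or 30 subjects are randomized into the study", whichever is first. Eligibility is reviewed again before infusion (Protocol 7.2), and SAP 8.6 and 8.8 provide for incomplete or attempted administration.

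**Analysis.** Efficacy is primarily analyzed in the mITT population (SAP 10), which excludes uninfused CAP-1002 subjects (SAP 6). Analyses in other populations are optional. In an ITT analysis, subjects missing both Month 6 and Month 12 changes are multiply imputed (5 data sets) from all observations, using the baseline value plus "Month 6 change from baseline, Month 12 change from baseline, and treatment group". An optional MNAR analysis imputes from usual care subjects only.

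**The concern.** There are two separate gaps.

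First, the protocol intends follow-up of everyone randomized, but the readable text gives a site no date from which to schedule an uninfused CAP-1002 subject. The SAP's planned day is a different rule in a document that sites do not work from, and it does not say which planned day counts after rescheduling.

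Second, the ITT population is the one that keeps every randomized subject as assigned, so it can show what assignment to CAP-1002 achieves when some infusions do not happen. If uninfused subjects have no outcomes, the CAP-1002 term of the imputation model is estimated from infused subjects alone. The imputed values then carry the infused effect, and the ITT result moves toward the mITT result by construction. Agreement between the two would say little about robustness.

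**Working it through.** **1. The SAP's own example.** Inputs (SAP 7.7): infusion 5 days after randomization, assessment 65 days after. Study day = 65 − 5 = 60, inside the Week 6 window (30 to 61). This reproduces the SAP.

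**2. The ITT anchor still needs Day 0.** Since X = Day 0 − randomization date, study day = observation − randomization − X = observation − Day 0. The randomization date cancels. If X were taken as 0 for want of a Day 0, the same assessment would be day 65 and fall in Month 3 (62 to 153).

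**3. Do the windows lose outcomes?** Month 6 (nominal 180) accepts days 154 to 275, a margin of 26 days early and 95 late. Month 12 (nominal 360) accepts 276 to 427, a margin of 84 early and 67 late. An error of a few weeks in Day 0 therefore need not make a value missing.

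**4. Imputation, by algebra.** Assume 12 infused, u uninfused, infused effect δ, uninfused effect 0, and all u missing both visits.
- Full-data ITT effect: 12δ/(12 + u).
- SAP model: imputed subjects receive about δ, so the estimate is (12δ + uδ)/(12 + u) = δ.
- Ratio: (12 + u)/12, which is arm size/12.

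If only k of the u are missing both visits, the ratio is (12 + u)/(12 + u − k). For u = 3 this gives 15/14 = 1.07 (k = 1), 15/13 = 1.15 (k = 2) and 15/12 = 1.25 (k = 3).

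**5. Imputation, by simulation.** The SAP 10 method was simulated: fully conditional regression on baseline, both changes and group, 20 iterations, 5 imputations, 1,500 trials per row. Assumptions: equal arms, infused effect 1, uninfused effect 0, all uninfused missing both visits. The Month 12 change was analyzed with baseline as covariate. Monte Carlo standard error is about 0.01.

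| Randomized | Uninfused / CAP-1002 arm | Arm/12 | Full data | SAP model | Usual-care-only imputation |
|---|---|---|---|---|---|
| 24 | 0/12 | 1.00 | – | – | – |
| 26 | 1/13 (7.7%) | 1.08 | 0.90 | 0.98 | 0.90 |
| 28 | 2/14 (14.3%) | 1.17 | 0.85 | 0.99 | 0.85 |
| 30 | 3/15 (20.0%) | 1.25 | 0.80 | 1.00 | 0.81 |

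In the 1/13 row both the full-data and SAP-model figures run slightly below the algebraic 12/13 = 0.92 and 1.00, because they share the same simulated data. Their ratio, 0.978/0.899 = 1.09, agrees with 13/12. The baseline slope and residual variance were pooled over both arms, as the SAP specifies, and this did not remove the effect.

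**The case against.** **Follow-up is intended.** A reader might infer that uninfused subjects are dropped. The documents do not support that: the protocol promises visits to all randomized subjects, and the Amendment 2 log records removal of a sentence that sent uninfused CAP-1002 subjects to early termination. If one is withdrawn, Protocol 7.11 still asks for Month 12 testing. What is missing is the date. Protocol 3.1 also contains a redacted block, so the absence of a fallback can be confirmed only for the readable text.

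**The SAP partly fills the gap.** Where an infusion was planned, SAP 7.6 yields a Day 0 for analysis. This stands, but the rule conflicts with the protocol and leaves Baseline undefined for these subjects when read literally.

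**Missing data do not follow from a missing anchor.** A reader might link the two gaps causally. Step 3 shows why that fails. The imputation issue arises only if both visits are missing for some other reason or are never scheduled, and SAP 10 expects very few missing observations.

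**The affected analysis is secondary.** Efficacy is exploratory, mITT is primary, ITT is optional, and no text says that ITT and mITT agreement will be read as robustness. This limits the importance of the point but does not correct the model.

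**The size is small against the noise.** The documents give no SD. If the infused effect were 0.5 to 1.0 SD (an assumption), the bias at 3 of 15 would be 0.1 to 0.2 SD, against a standard error near √(2/15) = 0.37 SD. At 1 of 13 it would be 0.04 to 0.08 SD. This stands.

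**Usual-care imputation is an estimand choice.** This is correct, and a reason to write the choice down.

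**Conclusion.** Both gaps hold. The Day 0 definitions in Protocol 7.2, Appendix 1 and SAP 7.6 conflict, and the protocol's definition gives an uninfused CAP-1002 subject no date for his visits. In an ITT analysis, an uninfused subject missing both Month 6 and Month 12 would be imputed at about the infused-arm mean.

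The overstatement is about 8% for 1 of 13 uninfused and at most 25% for 3 of 15, given 12 infused, equal arms, no benefit without infusion, and every uninfused subject missing both visits. If any of them has data, it is smaller (step 4). If 30 are randomized before 12 are infused, the uninfused share and the factor can be larger. The planned 24 subjects, 12 per arm, would imply none uninfused, and the 0% to 20% range is inferred from the enrollment stop, not forecast by the sponsor. A reader might take 25% as the expected bias of the trial's efficacy result. It is a worst case under these assumptions, for an optional analysis, and it does not touch the primary mITT estimate. The point should be corrected, but it does not threaten the main analysis.

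**What to change.** 1. **Day 0.** Reconcile Protocol 7.2, Appendix 1 and SAP 7.6 and 7.7, including the Baseline definition, by giving CAP-1002 subjects who are not infused one fixed fallback anchor. Randomization + 7 days is a natural example: usual care already uses it, and the Amendment 1 log says infusion was anticipated at that interval. Use it to time visits from the point at which non-infusion is known through Month 12. Items already past by then, such as Day 1 rhythm monitoring, should not count as deviations.
2. **Imputation.** In SAP 10, for any ITT analysis, impute the remaining missing outcomes of uninfused CAP-1002 subjects from usual care subjects. This adapts the usual-care-only method described for the MNAR analysis, which is not at present specific to uninfused subjects. Keep the current MAR model as a sensitivity analysis.

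The cost is a sentence or two in each document, visits the protocol already promises, and one imputation step specific to subject status. The ITT effect may come out slightly smaller. Obtaining real Month 6 and Month 12 values matters most, since it makes the imputation choice largely irrelevant.
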